## 1.0 Background

Up to 20% of the US population carries a label of penicillin allergy, the most commonly reported medication allergy. However, in the presence of appropriate skin and oral challenge testing in current practice only 4% or less of these allergy labels can be verified as accurate. Because most patients reporting allergy to penicillin aren't actually allergic their reported allergy leads to unnecessary avoidance of penicillins, treatment with less effective 2nd and 3rd line antibiotics with more side effects, and worsened outcomes. At Vanderbilt, in current practice, only 13.4% of patients ever get their penicillin allergy label removed, despite up to 96% being potentially able to tolerate a penicillin safely.

When asked about their history of penicillin allergy, most patients report symptoms that are considered low-risk by specialists in allergy. Low-risk penicillin allergies are routinely challenged by allergy doctors with test dose challenges, meaning a small dose of amoxicillin is given and the patient is observed. Patients who tolerate the medication during observation have their allergy label to penicillin removed from the chart. Test dose challenges are known to be safe in low-risk patients and are recommended as a tool in penicillin allergy evaluation by the American Academy of Asthma, Allergy and Immunology. Unfortunately, test dose challenges are not performed as a part of routine practice outside of the field of allergy due to most physicians being unfamiliar with the features of low-risk penicillin allergy and the procedure of performing a test dose challenge.

Therefore, we developed a risk stratification tool validated on the outcomes of penicillin allergy testing in the Vanderbilt Drug Allergy Clinic that can help physicians to identify low-risk penicillin allergy patients who would successfully tolerate a test dose challenge.

Our objective is to increase the familiarity with penicillin allergy history taking among physicians, and the rate at which low-risk penicillin allergies are tested and removed in current practice.

We plan to perform a stepped wedge cluster randomized trial of this best practices intervention to provide risk stratification and test dose amoxicillin challenges in patients who are at low risk of having an ongoing penicillin allergy, using our internally validated risk stratification tool.

We anticipate that this study will provide evidence that our approach is an effective strategy by which to implement current guidelines recommending the use of allergy evaluations and test dose challenges in hospitalized patients with low risk penicillin allergy. We anticipate that the current study will lead to further studies in specialized populations with a more frequent need for antibiotics, such as transplant patients, cancer patients, and immune deficient patients.

Improvements in the management of penicillin allergy will provide significant direct and indirect benefits to patients, society, and the healthcare system.

## **2.0 Rationale and Specific Aims:**

Currently it is estimated that at least 25 million people in the United States are labeled as penicillin allergic although less than 1.5 million of these are truly allergic. Although combined skin testing and oral challenge is an evidence-based de-labeling strategy the high burden of penicillin allergy labels means these services are available only through specialty allergy practices. There is therefore a need to provide evidence for alternative penicillin de-labeling strategies such as direct oral challenge. Previous studies have utilized quasi-experimental designs. Test dose challenges are currently recommended as a strategy for removal of low risk drug allergies, but the current experience is limited to single arm observational studies and evidence-based strategies for identifying low risk patients are lacking. Our objective is to demonstrate the benefit of providing risk stratification in removing penicillin allergy labels for low risk penicillin allergy patients in a randomized controlled trial.

Health literacy is the capacity of an individual to obtain and understand health information and services to make appropriate health decisions, and could play a role in a patient's decision to undergo testing for a penicillin allergy. We propose to use the Health Literacy Screening (HEALS) Database to determine if there is a difference in health literacy 1) between low-risk penicillin allergy patients who agree to versus refuse an amoxicillin challenge and 2) among low-risk challenge accepted, low-risk challenge refused, and higher-risk history patients. This information will help us determine if we need to adapt our communication strategies with patients approached for penicillin allergy label removal to be more accessible for patients with low or limited health literacy.

**We therefore aim to establish the safety, effectiveness, and impact of single dose oral challenge as a testing strategy to remove the label of low-risk penicillin allergy.**

## **3.0 Inclusion/Exclusion Criteria**

- Inclusion Criteria:
  - For Pilot Study: VUMC patients age 18 or older with a penicillin allergy reported in their chart and are medically stable, currently admitted to ICU.
  - For the RCT: VUMC patients age 18 or older with a penicillin allergy reported in their chart, and are medically stable, currently admitted to stepdown unit or regular floor bed.
- Exclusion Criteria: Patients with a penicillin allergy reported in their chart, but who are currently medically unstable. Patients who are pregnant.

## **4.0 Enrollment/Randomization**

Patients with penicillin allergy listed in their chart and admitted to a medical unit qualifying for intervention or control group during the study period will be enrolled in the study to the respective group that their unit is assigned to, with waiver of consent/authorization.

An initial pilot study will be performed in the medical ICU to demonstrate safety in a setting with the highest level of acute nursing and skilled support.

During the trial, randomization will occur using a stepped wedge cluster randomized controlled trial design. Medical units at VUMC will be assigned to clusters. A single cluster will be selected for intervention at the outset of the trial. Subsequent additional clusters will first contribute to the control group, and be selected to randomly cross over to the intervention group at regular 1-month intervals.

Randomization by medical unit with a stepped inclusion of additional medical units over time is the most equitable way of providing the study intervention, which we expect will provide a significant benefit compared to standard of care.

As penicillin allergy is a diagnosis that can affect people across differing age, sex, race/ethnicity backgrounds, we fully expect that patients will receive equitable inclusion due to the randomized nature of our study.

## **5.0 Study Procedures**

Pilot Study: The teams caring for eligible penicillin allergic patients admitted to the ICU will be provided with the study intervention, as described below.

Control Arm: The current standard of care in hospitalized patients with reported penicillin allergy is to do nothing, versus direct challenge with amoxicillin when an allergy history is perceived to be sufficiently low risk, versus obtaining an allergy consultation for help with management, at the discretion of the primary team. Hence, no intervention will be provided.

Intervention Arm: The intervention will provide access to a best-practices alert containing a penicillin allergy risk stratification tool and an oral amoxicillin test dose challenge orderset for patients who stratify as low risk. The risk stratification tool has been demonstrated retrospectively to have a >99% (95% CI 96.4,99.9) negative predictive value for the presence of penicillin allergy in those who stratify as low risk. Test dose challenges are a recommended part of routine practice in patients who report allergy but have symptoms that are low risk for true or ongoing allergy.

Scenario: For patients who qualify for intervention in a unit randomized to intervention, the following best practice alert or a similar alert will be provided to the rounding physician.

"Did you know that 96-99% of patients of patients labeled as allergic to penicillin can safely tolerate these drugs? Use our tool to determine if your patient is low risk (<1% likely to have a positive allergy skin test) and can be considered for a potential challenge with amoxicillin to remove this allergy label. ([Link to tool](#))."

The embedded link will provide an online risk stratification tool that will allow treating physicians to assess if their patient is low risk. For patients who stratify as low risk, information on oral challenges with amoxicillin and the name of an order set that contains the necessary elements for an oral challenge with amoxicillin will be provided (250mg amoxicillin PO x 1 dose, epinephrine at bedside, vital signs at baseline and q 30 minutes x 2.) For patients whose penicillin allergies stratify as higher or highest risk, information will be provided on the management of these penicillin allergies, with or without consultation from the allergy service. **Treatment decisions on whether to act on the provided information will be made by the treating physician and the patient.**

## **6.0 Reporting of Adverse Events or Unanticipated Problems involving Risk to Participants or Others**

Data and Safety Monitoring: Given there are minor potential risks to participants in the proposed trial with waiver of consent, it will be performed with monitoring and review by Vanderbilt University Medical Center IRB and under the guidance of the Vanderbilt Institute for Clinical and Translational Research. We propose to implement an overseeing data and safety monitoring plan that includes the appointment of [name], MD as an independent data safety monitor.

Investigator Training and Involvement:

- 1) All investigators, research coordinators, and other staff will complete and maintain training in the protection of human research subjects.
- 2) All persons accessing trial data, will in addition to the above, complete appropriate institutional training.
- 3) The physician leader at Vanderbilt ([name]), will be available to treating physicians who might implement the best practice alert in order to provide additional information about the study, including risks, benefits and alternatives, and to answer questions as needed.
- 4) All investigators and staff involved with patient care will remain updated on issues related to patient rights and safety through educational programs and updates provided by the institutions.

Data Handling/Confidentiality

- 1) Training outlined above addresses issues of confidentiality in research.
- 2) All patients will be assigned a study number and de-identified upon entering the study. A master list linking the patient identifying information such as the electronic health record and de-identified study identification will be kept under double-lock and key at each site with an access log required for when the list is accessed. A computer that is password-protected and behind a restricted, locked office door will also be acceptable.
- 3) All patient records for the research study will be maintained on the HIPAA-compliant server where the completed case report forms are kept or similarly on the HIPAA-compliant cloud server for photographs. To ensure accuracy, data will be checked and reviewed by research staff. Audits of the data will be done by the Vanderbilt Coordinating Center to ensure quality and completion of the forms.

4) Only de-identified data will be electronically transmitted and this will be done using institutional encryption procedures.

#### Adverse Events

1) Exclusion criteria include patients who are currently medically unstable and unable to receive study procedures, or patients whose primary care is received outside of Vanderbilt University Medical Center. We know that by restricting inclusion to patients who receive the majority of their care at Vanderbilt that this will enable better long term monitoring of adverse events via the EHR.

2) All adverse events will be discussed with and evaluated by a physician investigator as soon as the subject or study personnel report them.

3) Adverse events including SAEs upon initial amoxicillin challenge or upon subsequent administration of penicillin class drugs in patients whose penicillin allergy label has been removed, or any unanticipated problems will be appropriately reported to the IRB, safety monitor, and NIAID. In addition to the IRB review of adverse events outlined above, the PIs will meet at least quarterly with staff to discuss any problems that arise that could compromise patient safety. Meetings will be held more frequently to quickly rectify problems if they arise. When necessary, the IRB will be consulted for further guidance. This is particularly true for reactions, which, in their most severe forms, threaten life or function. A serious AE (SAE) or serious adverse drug experience (SADE) is any untoward medical occurrence that:

- Results in death
- Is life-threatening. "Life-threatening" refers to an event in which the subject is at risk of death at the time of the event; it does not refer to an event which hypothetically might have caused death if it were more severe (ICH E6).
- Requires inpatient hospitalization or prolongation of existing hospitalization
- Results in persistent or significant disability/ incapacity (as per reporter's opinion)
- Is a congenital anomaly/birth defect
- Is another medically important condition. Important medical conditions that may not result in death, be life-threatening or require hospitalization may be considered as SAEs or SADEs when, based upon appropriate medical judgment, they may jeopardize the subject or may require intervention to prevent one of the outcomes listed in the definition above. Examples of such events relevant to this trial are urticaria, angioedema, respiratory distress, prolonged nausea or vomiting after direct provocation testing with amoxicillin that might be the prelude to anaphylactic shock. [Code of Federal Regulations Title 21, Volume 5, 21CFR312.32, revised April 1, 2006].

4) The PI, staff, and the research coordinators (or qualified persons providing coverage) will be available 24 hours each day to participants and other investigators, should an emergency arise.

5) The Vanderbilt Coordinating Center will submit an annual safety and adverse event report to the NIAID program official and the Vanderbilt IRB.

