## 2. PARTICIPANTS AND TREATMENT ARMS

Adult patients admitted to hospital during the 12-month study period who had 24-hour exposure to any of the study units will be included if they are not known to be pregnant. Pregnancy status is based on either documented known pregnancy via ObGyn status or BhCG results that are classified as positive using VUMC laboratory cutoffs.

Participants will be in either the control group or the intervention group, depending on when they presented to the hospital, and which hospital unit they were exposed to. Specifically:

- Control Group: Any patient who did not have a 24-hour exposure to a study unit where the intervention was active but did have at least 24-hour exposure to a control unit. The current standard of care in hospitalized patients with reported penicillin allergy is to do nothing, with all care at the discretion of the primary team. Hence, no intervention will be provided.
- Intervention Group: Any patient who had a 24-hour exposure to a study unit at any time where the intervention was active. The intervention includes systematic identification those with a penicillin allergy, application of a penicillin allergy risk stratification tool, and use of an oral amoxicillin test dose challenge order set for patients who stratify as low risk. The risk stratification tool has been demonstrated retrospectively to have a >99% (95% CI 96.4,99.9) negative predictive value for the presence of penicillin allergy in those who stratify as low risk. Test dose challenges with amoxicillin are a recommended part of routine practice in patients who report allergy but have symptoms that are low risk for true or ongoing allergy. When a unit crosses over and becomes a “live” unit with the intervention, a patient who was already admitted on the unit needs to be present for 24 hours afterward to be considered exposed to the intervention.

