### Key secondary endpoints

The secondary endpoints for this trial include the following:

1. Tolerance of an amoxicillin oral challenge, which will be documented using a smart phrase to indicate tolerance or intolerance. This outcome is a binary variable, either yes= tolerated, or no =not tolerated, with relevant symptoms to be determined by chart review.
2. Uptake of the risk stratification tool: This is determined by whether patients with a penicillin allergy label in their chart receive a risk assessment. This is a binary variable, either the patient did or did not receive a risk assessment of their penicillin allergy.
3. Amoxicillin adverse events: In patients who did not tolerate their amoxicillin oral challenge, we will assess the types of adverse events that were reported.
  - a. An immediate allergic amoxicillin challenge adverse event will be defined as an adverse event reported in association with the amoxicillin challenge that includes symptoms of anaphylaxis or rash, with onset within 6 hours of the challenge dose being given.
  - b. A non-immediate allergic amoxicillin challenge adverse event will be defined as an adverse event such as rash that is potentially consistent with allergy, occurring within 24 hours of the dose being given.
  - c. A non-allergic amoxicillin challenge adverse event will be defined as an adverse event, such as gastrointestinal upset, reported in association with amoxicillin challenge, within 6 hours of the challenge dose being given.
4. Communication about penicillin allergy label removal in the discharge summary: This is determined by the presence of language about the penicillin allergy evaluation, challenge, and removal, in those patients who underwent penicillin allergy challenge. The outcome is a binary variable, as this information is either present, or absent.
  - a. This data will be obtained by manual chart review.
  - b. A smart phrase has previously been created that was encouraged to be used for this purpose, and its utilization will be extracted.
5. Longer term penicillin allergy label removal, over 3 months and 18 months of follow up. Among those who underwent a penicillin allergy label removal, whether the allergy remains out of the chart or is “ever/never” re-entered into the chart. The outcome is a binary variable at either 3 months or at 18 months.

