6. Time to penicillin allergy return: for those participants who underwent an allergy label removal, we will compare the time to return of the allergy label based on the date the label first re-appeared in the chart.
7. Antibiotic utilization: This is based on the presence of qualifying penicillin or cephalosporin treatment doses, during the same hospitalization, and at 3 months and 18 months of follow up.
  - a. Same hospitalization: Utilization of these antibiotics will be defined as “yes” or “no” during the initial hospitalization in which amoxicillin challenge could have occurred, as a binary variable.
  - b. Subsequent utilization: Utilization of these antibiotics will be defined as “ever/never” by 3 months and ever/never by 18 months of follow up, as a binary variable.
  - c. Drugs included in the definition of penicillins are predefined as:
    - i. Ampicillin
    - ii. Ampicillin/sulbactam (unasyn)
    - iii. Amoxicillin
    - iv. Amoxicillin/Clavulanate (augmentin)
    - v. Cloxacillin
    - vi. Dicloxacillin

- vii. Nafcillin
- viii. Penicillin G
- ix. Penicillin VK
- x. Piperacillin
- xi. Piperacillin/Tazobactam
- xii. Ticarcillin
- xiii. Ticarcillin/Clavulanate (timentin)

d. Drugs included in the definition of cephalosporins are predefined as:

- i. Cefadroxil
- ii. Cefprozil
- iii. Cefaclor
- iv. Cephalexin
- v. Cephalothin
- vi. Cefazolin
- vii. Cefoxitin
- viii. Cefotetan
- ix. Cefamandole
- x. Cefuroxime
- xi. Cefepime
- xii. Ceftriaxone
- xiii. Cefpodoxime
- xiv. Ceftazidime
- xv. Cefdinir
- xvi. Cefixime
- xvii. Ceftaroline
- xviii. Ceftobiprole
- xix. Ceftozolane-Tazobactam

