## **9. DEFINITION OF ANALYSIS SETS**

### **Intent-to-treat Analysis Set**

All participants who were present on a study unit for at least 24 hours during the 12-month study period will be included in the intent-to-treat analysis set. The intent-to-treat participants will be used for all primary, secondary, and other efficacy analyses. All participants will be included in the intent-to-treat analysis set, regardless of what interventions or challenges were given.

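### The protocol relies on excluding patients with primary care outside VUMC for long-term EHR monitoring, but its eligibility section and the SAP analysis sets omit that exclusion, and the 3- and 18-month endpoints have no rule for patients who do not return

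*Protocol*

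**What the plan says.** Protocol section 6.0, Adverse Events, item 1, names as an exclusion "patients whose primary care is received outside of Vanderbilt University Medical Center". The reason given is that "this will enable better long term monitoring of adverse events via the EHR".

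Protocol section 3.0 gives the exclusions as "Patients with a penicillin allergy reported in their chart, but who are currently medically unstable. Patients who are pregnant". Its pilot inclusion bullet begins "VUMC patients age 18 or older with a penicillin allergy reported in their chart and are medically stable", and the trial bullet opens in nearly the same words. The term for VUMC patients is not defined, and nothing ties it to where primary care is received.

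SAP section 2 says: "Adult patients admitted to hospital during the 12-month study period who had 24-hour exposure to any of the study units will be included", provided they are not known to be pregnant. SAP section 9 defines the intent-to-treat set in the same way: "All participants who were present on a study unit for at least 24 hours during the 12-month study period will be included". It assigns that set to all primary, secondary and other efficacy analyses.

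Three SAP key secondary endpoints look beyond discharge:

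- **Endpoint 5** is whether a removed label is re-entered in the chart: "The outcome is a binary variable at either 3 months or at 18 months".
- **Endpoint 6** is time to label return, dated from the label's first reappearance in the chart.
- **Endpoint 7b** is later penicillin or cephalosporin use, scored at 3 months and as "ever/never by 18 months of follow up, as a binary variable".

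Protocol section 6.0 (Adverse Events, item 3) also commits to reporting reactions to later penicillins in de-labelled patients, and section 8.0 lists tolerance of penicillins at 3 to 18 months.

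**The concern.** There are two linked problems. The first is a contradiction about eligibility: one protocol section relies on an exclusion that the sections defining the trial population and the analysis sets do not contain.

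The second is what follows if the exclusion is not applied. Label re-entry, antibiotic doses and later reactions are seen only if the patient has contact with VUMC. The SAP does not require contact during the window, has no category for patients who could not be observed, and states no censoring rule for time to label return. A patient who never comes back has no event on record. Read literally, the ever/never definitions then give never, and the Cox model has no event.

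Multiple imputation is optional in the SAP and covers missing outcomes, but missing is not defined. It would help only if such patients were first classed as missing.

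At stake are the durability of de-labelling, later antibiotic use, and long-term tolerance of penicillins. These are secondary outcomes, but they bear on the safety and impact parts of the protocol's stated aim.

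**Working it through.** The plan gives no figure on this point to reproduce. The check is a comparison of the texts, followed by an illustration on assumed rates.

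**1. Is the exclusion present?**

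| Place | Exclusion for outside primary care |
|---|---|
| Protocol 6.0, Adverse Events, item 1 | Yes |
| Protocol 3.0, eligibility | No |
| SAP 2, population | No |
| SAP 9, intent-to-treat set | No |

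All four are current text.

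**2. Does the SAP deal with unseen patients elsewhere?** Only descriptively. The Main Analysis section of SAP section 10 lists counts of later VUMC encounters and a ratio of penicillin treatments to encounters. Neither is used to decide who is observable for endpoints 5, 6 and 7b.

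**3. Label durability.** Let u be the share of patients who are unseen and read as never. If unseen and seen patients have the same true rate, then

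observed rate = true rate × (1 − u).

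The documents do not give u; a range of 10% to 50% is assumed here. True re-entry is assumed to be 20%.

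| u | Observed re-entry | Apparent durability |
|---|---|---|
| 0% | 20% | 80% |
| 10% | 0.20 × 0.9 = 18% | 82% |
| 30% | 0.20 × 0.7 = 14% | 86% |
| 50% | 0.20 × 0.5 = 10% | 90% |

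Endpoints 5 and 6 apply only to patients whose label was removed. The SAP assumes 0.5% removal in controls, so durability is in effect a one-arm rate and the error does not cancel between arms.

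**4. Later antibiotic use, equal loss in both arms.** Assumed true use is 20% (control) and 35% (intervention).

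| u | Control | Intervention | Difference (points) | Odds ratio |
|---|---|---|---|---|
| 0% | 20% | 35% | 15 | 2.15 |
| 10% | 18% | 31.5% | 13.5 | 2.09 |
| 30% | 14% | 24.5% | 10.5 | 1.99 |
| 50% | 10% | 17.5% | 7.5 | 1.91 |

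The risk ratio stays at 1.75 throughout. The odds ratio, which is the SAP's effect measure, moves modestly towards 1.

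**5. Later antibiotic use, unequal loss.** Assume true use of 30% in both arms, so no effect.

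- Unseen 20% (control) and 30% (intervention): observed 0.30 × 0.8 = 24% and 0.30 × 0.7 = 21%. Odds ratio = (0.21/0.79)/(0.24/0.76) = 0.84.
- The reverse: 21% and 24%, odds ratio 1.19.

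Unequal contact can therefore produce an apparent effect in either direction.

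**6. Would censoring at the last VUMC encounter solve it?** No. Label return is recorded at encounters, so a patient stays at risk only while a further encounter is still to come. In a simulation with complete follow-up, 0.15 encounters per month and a 10% chance of re-entry at each (all assumed), true re-entry by month 17 is 1 − exp(−0.15 × 0.10 × 17) = 22.5%. Kaplan-Meier with censoring at the last encounter gave about 36%.

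**The case against.** **The stated reason is narrow.** Protocol section 6.0 gives adverse-event monitoring as the purpose. This stands: a reader might infer that the exclusion was written to protect label durability and antibiotic use, and the text does not say so. The extension is an inference from the fact that these outcomes also depend on what the record shows.

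**Silence does not prove the exclusion was dropped.** SAP sections 2 and 9 do not list a penicillin label or medical stability as entry conditions either, so they are incomplete restatements of eligibility. This stands too. The documents do not establish that patients with outside primary care are in the analysed cohort, only that it is unclear which text governs.

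**Scoring as never is not written.** Correct. It is what the definitions give when no event is on record. The defect is an unspecified rule, and no-contact patients could still be classed as missing.

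**Endpoints 5 and 6 are chart states.** For a patient who never returns, a label still absent from the VUMC chart is literally true. But a rate defined that way describes lasting de-labelling only among patients with an opportunity to be relabelled, so the share without contact has to be shown.

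**The SAP chose the intent-to-treat set for secondary analyses.** That is a legitimate choice, and a restricted analysis should stand beside it and not replace it.

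**Conclusion.** The contradiction over eligibility is established from the text. The consequence for the long-term endpoints is conditional: if the exclusion is not applied, and patients who do not return are left as never, then durability is overstated and absolute later antibiotic use is understated. Later penicillin reactions would be under-recorded for the same reason. The arm comparison of later use can be biased either way if contact differs by arm.

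The size is unknown. The share u is the proportion with no later VUMC contact, which is not the same as the proportion with outside primary care, and the documents give neither. The 20%, 30% and 35% rates are assumptions as well.

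Two stronger readings are not supported. A reader might infer that any arm difference must be understated; the unequal-loss case shows otherwise. A reader might also infer that the trial's main result is affected. The primary endpoint is fixed before discharge, so its ascertainment does not depend on return; only the population it describes is left unclear.

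This should be corrected, but it concerns secondary and long-term safety outcomes only.

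**What to change.** 1. Reconcile protocol section 6.0 with section 3.0 and with SAP sections 2 and 9. State whether outside primary care is an exclusion and define it once. Section 6.0 uses both primary care and majority of care, and these are not the same criterion.
2. Keep the intent-to-treat set for the primary endpoint and as the stated set for the secondary endpoints.
3. For SAP endpoints 5, 6 and 7b, pre-specify an analysis beside it restricted to patients with VUMC primary care at baseline. The protocol already names this criterion, and it is fixed before exposure. It should reduce unseen follow-up but will not remove it.
4. Report, by arm, the share with no VUMC encounter in the 3-month and 18-month windows, from the encounter counts the SAP already collects.
5. For time to label return, fit the Cox model in the same baseline-restricted set with administrative censoring. Do not censor at the last VUMC encounter.

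The cost is SAP and protocol wording, one baseline EHR variable to extract (primary-care site is not in the SAP's list of baseline variables), and wider intervals in the restricted analysis of these secondary endpoints.
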